Study design	This is a interventional, multicenter, non-randomized, parallel-group, opened designed study lasting during 12 months for approximately 130 patients with type 2 diabetes and obesity.
Population	The study is expected to include approximately 100 patients with T2DM and obesity who will be on active management and another 30 patients whose case records will be collected from routine clinical practice for comparison purposes.
Inclusion criteria	
 • Signed Informed Consent. Written informed consent must be obtained before any assessment is

	
performed.
 
 • ≥ 18 years • Type 2 diabetes • The Body Mass Index is from 28 to 40 kg/m²
Exclusion criteria	
 • Pregnant or nursing (lactating) women, where pregnancy is defined as the state of a female after conception and until the termination of gestation. • Type 1 diabetes • Proliferative retinopathy • Renal impairment: serum creatinine >1.5 mg/dL, creatinine clearance < 40 ml/min and/or proteinuria • The lack of ability to perform the physical exercises due to the orthopedic or cardiovascular disorders • Chronic alcoholism, acute alcoholic intoxication
Investigational and reference therapy	
No drugs will be supplied during the study. Hypoglycemic drug therapy will be provided according routine standard practice without any special changes.

Efficacy assessments	
 • Weight reduction • Control of glycemic in HbA1C and FPG • Blood pressure • Lipid profile indicators
Safety assessments	
 • Adverse events • Vital signs • Laboratory assessments • ECG
Other assessments	
 • HE supply form • Survey for hypoglycemic assessment • Scale of individual perception of physical exercises (Borg scale)
Data analysis	
Descriptive statistics will be applied in the study to describe the sample size of the patients at baseline and at follow-up visits, demographic data recorded during the examination of the study parameters, as well as their changes.
 
The primary analysis of the proportion of the patients with response on the treatment will be performed using multivariate logistic regression and calculating odds ratios with corresponding 95% CI. To control the potential confounding factors, age, sex, BMI, disease duration, the baseline values of HbA1c will be taken into account in the regression model.

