7.6 Risks and benefits

The risk to subjects in this trial will be minimized by compliance with the eligibility criteria and study procedures, close clinical monitoring.

There are no therapy changes or innovations in this study. The drug therapy administration is carried out strictly in accordance with the approved instructions for medical use, only with the registered indications and in accordance with appropriate clinical practice.

The study is designed to establish for patients with T2DM and obesity the reduction of the body weight, improvement of glycemic and lipid metabolism, and reducing blood pressure level. We expect that the study can improve a QoL and reduce diseases complications in the study populations. Nvs survey on hypoglycemia will be used to assess the quality of life in patients (**Appendix 2**).

8 Population

The study is expected to include approximately 100 patients with T2DM and obesity. It is planned to have 100 patients in the active group who will be on active life style management; the control group will be 30 patients who will be matched with active group in terms of their indicators. Both groups will receive standard drug therapy for diabetes.

The control group should match the active group. The following criteria should be taken into account (criteria of inclusion and exclusion): match in BMI (<30; ≥30) and baseline HbA1c (<7.5; ≥7.5). The decision to include a patient into active or control group should be made by a doctor.

Drop-out of patients is expected for about 20% of patients compared with the originally included population. The drop-out criteria is three in a row missed group classes in the first 12 weeks of the study in active group.

The drop-out in control group is not expected.

Patients will be distributed among two participating research centers.

The study will be executed in two sites, the [REDACTED] in Moscow and the [REDACTED] in Kazan. The adult patients with T2DM (men and women at the age of more than 18 years) will be under the observation if they need in the active weight loss according to the physician's decision and if a doctor decides that the active approach is necessary.

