An investigator must ensure that the participation in the study will be offered only to the patients, which meet the criteria for the study participation. To ensure the representativeness of the sample size, an investigator should not use any additional exclusion criteria; in addition, he/she must provide equal access to the study participation for all patients suitable for inclusion criteria. Drug therapy administration should be based exceptionally on the medical indications and should not aim at the inclusion of the patient in the study.

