8.1 Inclusion criteria

Patients eligible for inclusion in this study have to fulfill all of the following criteria:

1. Signed Informed Consent Form (**Appendix 3 and 4**). Written informed consent must be obtained before any assessment is performed.
2. Signed Informed Consent Form of doctor-ophthalmologist (**Appendix 5**) and cardiologist (**Appendix 6**) about inclusion of the patient *.
3. Men and women at the age of 18 years and older
4. Type 2 diabetes
5. The Body Mass Index is from 28 to 40 kg/m²

The objective to have a signed consent form from ophthalmologist and cardiologist is to ensure the patient can practice physical exercises and the level of physical activity for a patient (active, with limitations and what particular limitations) based on the existing condition – if cardio-vascular diseases are present. Consultation of ophthalmologist and cardiologist should be conducted before patients are included in the study. Medical specialists will be selected from the existing research center staff (Moscow and Kazan) where the study will be conducted.

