8.2 Exclusion criteria

Patients fulfilling any of the following criteria are not eligible for inclusion in this study. No additional exclusions may be applied by the investigator, in order to ensure that the study population will be representative of all eligible patients.

1. Pregnant or nursing (lactating) women, where pregnancy is defined as the state of a female after conception and until the termination of gestation.

2. Type 1 diabetes
3. Proliferative retinopathy, hemorrhage and peeling of a retina.
4. Renal impairment: serum creatinine >1.5 mg/dL, creatinine clearance < 40 ml/min and/or proteinuria
5. The lack of ability to perform the physical exercises due to the orthopedic or cardiovascular disorders*
6. Chronic alcoholism, acute alcoholic intoxication.

*The criteria is only applicable to the active group.

9 Treatment

Hypoglycemia drug therapy will be applied to the study participants according to the routine clinical practice, no limitations to correct the therapy (for the reason a patient takes part in the study) is implied.

The drug therapy administration is carried out strictly in accordance with the approved instructions for medical use, only with the registered indications and in accordance with appropriate clinical practice.

The investigator should inform the patients that in case the patient change their therapy or take new drugs the patients should inform the investigator. All drugs (including non-patterned name, dosage, first and end date of intake) and clinically significant non-medical therapy that are used by the patients to treat diabetes at the moment the patient enters the trial should be registered in eCRF.

10 Visit schedule and assessments

Patients will be subject to a comprehensive evaluation of health and functional status.

The main parameters, which should be measured in accordance with the periodicity adopted in routine practice:

- BMI and body weight
- Waist circumference, ratio between waist and hip
- HBA_{1C}, FPG
- BP (SBP, DBP)
- Lipid profile (cholesterol, triglycerides, LDL, HDL)
- The number of DM related hospitalizations
- QoL data via filling of questionnaires
- HE data (**Appendix 7**)

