- Contraindications and precautions for use are in general the same as for PhA and type 1 DM (see. Section 5.1.4. Recommendations), and are defined by DM complications and comorbidities.
- Additional factors limiting PhA in case of type 2 DM: coronary artery disease (CAD), diseases of the respiratory system, joints and others.
- The CAD risk requires mandatory electrocardiography (ECG) (according to the indications - stress tests, etc.) before starting PhA study.

In patients with type 2 DM, receiving insulin or oral hypoglycemic agents stimulating the insulin secretion (and very rarely - other hypoglycemic agents) PhA can cause hypoglycemia.

Education and self-control are carried out with the assistance of the clinical psychologist should be in compliance with the principles provided in the Russian algorithms (6th edition, 2013, Chapter 7, Education of the patients with DM).

Observation period is 12 months. The objective is to reduce weight no less than 5% compared with the baseline in the first three months and then to maintain the positive dynamics in the next 9 months.

Weight reduction will help to improve the metabolism of carbohydrates and lipids as well as to reduce the risk of complications.

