6.2 Exclusion criteria

Patients fulfilling any of the following criteria are not eligible for inclusion in this study:

1. Pregnant or nursing (lactating) women, where pregnancy is defined as the state of a female after conception and until the termination of gestation.
2. Type 1 diabetes
3. Proliferative retinopathy, hemorrhage and disinsertion of retina
4. Renal impairment: serum creatinine >1.5 mg/dL, creatinine clearance < 40 ml/min and/or proteinuria.
5. The lack of ability to perform the physical exercises due to the orthopedic or cardiovascular disorders *
6. Chronic alcoholism, acute alcoholic intoxication

* - the criterion is applicable only for the active group.

7 Population determination for statistical analysis

- All enrolled patients: all patients who signed informed consent for inclusion in the study. The population will be used for the disposition data summaries and listings.
- Safety Population: all patients of the active group included in the study, who started participating in the lifestyle correction program, and all patients of the

control group for whom the observation was started. The population will be used to summarize adverse events and other safety parameters.

- Full Analysis Set (FAS): all patients who provided baseline data and data to evaluate at least one efficacy parameter after the onset of observation. The population will be used for efficacy analyses.
- Per Protocol Set (PP): all FAS patients who did not have any major protocol deviations. The population was used to analyze the primary endpoint (sensitivity analysis).

The patient can be excluded from the Per Protocol Set for the following reasons:

- did not attend more than 3 consecutive classes in the active group;
- missed at least 50% classes of the program;
- did not provide data for the estimation of the primary endpoint.

8 General considerations

The latest available estimates before the start of the program for the active group and data from the Visit 1 for the control group will be used as the baseline values for the analysis of quantitative efficacy and safety parameters. The baseline visit is Visit 2 (Week 1) for the active group and Visit 1 for the control group.

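### Patients unable to exercise can enter only as controls, and neither the planned matching nor the named model covariates are designed to remove that difference

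*Protocol*

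**What the plan says.** - **Eligibility.** Exclusion 5 reads "The lack of ability to perform the physical exercises due to the orthopedic or cardiovascular disorders". Protocol 8.2 limits it by footnote: "The criteria is only applicable to the active group". SAP 6.2 does the same: "the criterion is applicable only for the active group". The Protocol synopsis lists the exclusion with no such limit.
- **Allocation.** Protocol Section 8: "The decision to include a patient into active or control group should be made by a doctor". Sites may not close the gap themselves. Section 8 says "an investigator should not use any additional exclusion criteria", and Section 8.2 says "No additional exclusions may be applied by the investigator".
- **Matching.** Protocol Section 8 and SAP Section 6 name two factors, BMI (below 30 or not) and baseline HbA1c (below 7.5 or not). SAP Section 6 also asks in general terms for comparability on core baseline parameters.
- **Models.** Protocol Section 13 and the primary model in SAP 12.1 name age, sex, BMI, disease duration and baseline HbA1c. The SAP introduces these as examples; the Protocol gives them as the list. The GEE sensitivity model selects from the same five.
- **Records of exercise capacity.** Protocol 8.1 requires an ophthalmologist's and a cardiologist's agreement, partly to establish "the level of physical activity for a patient (active, with limitations and what particular limitations". That criterion has an asterisk but no active-only footnote in the text supplied, and the consultation is to take place before inclusion. SAP 6.1 makes the same criterion active-only. The Borg scale is active-only (SAP Section 13). Protocol Section 10 promises an evaluation of functional status with no group limit.
- **Limiting conditions.** Protocol Section 10 notes: "Additional factors limiting PhA in case of type 2 DM: coronary artery disease (CAD), diseases of the respiratory system, joints and others".

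**The concern.** The control cohort is there to show a change from standard of care, and the primary result is a between-group odds ratio for at least 5% weight loss. An eligibility rule that admits one kind of patient to one group only builds in a difference between the groups before any programme effect. Here the rule concerns exercise, which the Protocol itself says helps to reduce and maintain body weight. If patients unable to exercise lose 5% less often under routine care, the control response rate falls for a reason unrelated to the programme, and the odds ratio overstates the benefit. With only 30 controls, a few such patients can move the estimate.

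**Working it through.** **Who can enter where.** A patient unable to exercise is barred from the active group and eligible as a control. A patient with lesser limitations can enter either group, because Protocol 8.1 provides for activity with limitations. The difference therefore concerns inability only.

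**What the plan gives.** It gives no response rates and no expected number of unable controls. Its sample-size statement (100 and 30 patients, 80% power) therefore says nothing about this point, and every rate below is an assumption.

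**Formulas.** Let *f* be the share of the 30 controls who are unable.
- Control rate *p* = (1 − *f*) × rate in able + *f* × rate in unable.
- With 50% active response the active odds are 1, so OR = (1 − *p*)/*p*. The OR against able controls only is the reference.
- SE(log OR) = √(1/25 + 1/(30 *p*(1 − *p*))), where 25 = 100 × 0.5 × 0.5.

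| Able / unable response | *f* | *p* | OR (reference) | Change | SE | Shift in log OR ÷ SE |
|---|---|---|---|---|---|---|
| 25% / 25% | any | 25.0% | 3.00 (3.00) | 0 | 0.467 | 0 |
| 25% / 20% | 10% | 24.5% | 3.08 (3.00) | +3% | 0.469 | 0.06 |
| 25% / 10% | 10% | 23.5% | 3.26 (3.00) | +9% | 0.475 | 0.17 |
| 25% / 20% | 30% | 23.5% | 3.26 (3.00) | +9% | 0.475 | 0.17 |
| 25% / 10% | 30% | 20.5% | 3.88 (3.00) | +29% | 0.494 | 0.52 |
| 15% / 5% | 10% | 14.0% | 6.14 (5.67) | +8% | 0.563 | 0.14 |
| 15% / 5% | 30% | 12.0% | 7.33 (5.67) | +29% | 0.596 | 0.43 |

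Example: 0.9 × 25% + 0.1 × 10% = 23.5%; 0.765/0.235 = 3.26; ln(3.26/3.00) = 0.082; 0.082/0.475 = 0.17.

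**Do the five covariates remove it?** In large simulated samples (25% / 10%, *f* = 30%), the log-odds of inability rose by 0, 0.5 or 1.0 per SD of age and of BMI. The five-covariate model gave an OR of 3.73 to 3.91. Adding an indicator for inability, or restricting to able controls, gave 2.97 to 3.03.

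**Price of restricting to able controls.** The right comparator is the planned analysis, which includes the unable controls.
- 27 able controls at 25%: SE = √(1/25 + 1/(27 × 0.1875)) = 0.487. Against 0.475 and 0.469 this is 2.7% and 3.9% wider; the 15% / 5% case gives 2.1%.
- 21 able controls at 25%: SE = 0.542. Against 0.494 and 0.475 this is 9.6% and 14.2% wider; the 15% / 5% case gives 7.8%.
- With equal response there is no bias to remove, and the widening is 4.4% (27) or 16.2% (21).

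RMSE of the log OR, √(SE² + shift²), planned v restricted, for able response 25%:
- Unable 10%: 0.482 v 0.487 (*f* = 10%); 0.557 v 0.542 (*f* = 30%).
- Unable 20%: 0.470 v 0.487 (*f* = 10%); 0.482 v 0.542 (*f* = 30%).

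Among these four settings, restriction wins only with the large share and the strong contrast.

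**The case against.** The best defence is that the effect may be trivial. At 10% unable the shift is 0.06 to 0.17 of a standard error, and nothing supports 30%. SAP Section 3 expects no significant weight reduction in controls. With lower control rates the shift is smaller relative to sampling error: at 5% able and 1% unable it is 0.10 SE (*f* = 10%) and 0.29 SE (*f* = 30%). This stands, and it limits how much weight the point can carry.

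A reader might infer that exercise capacity is not recorded for controls. The documents do not support that. Protocol 8.1 as supplied does not confine the specialist consultation to the active group, and Section 10 promises a functional evaluation for patients generally. Cardiovascular disease, stroke, neuropathy and diabetic foot are recorded as history, and SAP 12.2 plans a physical examination in both groups. The control schedule (Table 7-2) is not in the text supplied. It can be said only that recording is not clearly shown. Even where a record exists, no planned model names it.

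The general call for comparable groups does not close the gap, since the named matching factors are BMI and HbA1c and the footnote expressly admits unable controls.

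The synopsis is abridged (it also omits the specialist agreement), so that mismatch is editorial. It still needs correcting. Excluding unable controls also makes the cohort less typical of routine practice. That is a fair cost, but the remaining controls would still receive routine care.

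**Conclusion.** The structural point holds on the text: the plan as written admits patients unable to exercise to the control group only, and neither the matching nor the five named covariates is designed to correct for it.

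The direction is conditional. The odds ratio favours the programme only if unable controls respond less often than able ones. The Protocol's remark on physical activity makes this plausible but does not establish it under routine care. The size is unknown: under the 25% able-control scenarios with lower response in unable controls, +3% to +9% in the odds ratio at 10% unable, and +9% to +29% at 30%.

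Two stronger conclusions are not supported: that the primary result is biased whatever the controls' responses, and that controls are less fit than active patients in general. The rule concerns inability alone, and patients with lesser limitations can enter the active group. The point merits a change because the remedy is small, not because a large bias has been shown.

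**What to change.** 1. **Reconcile the texts.** Align the Protocol synopsis, Protocol 8.1 and 8.2, and SAP 6.1 and 6.2 on which group each exercise-related criterion applies to, and use the same exercise-ability criterion for both groups.
2. **If controls are already enrolled**, which the past tense in SAP 12.2 suggests, define inability by the wording of exclusion 5. Classify the 30 controls from baseline records: medical history, diabetes complications, physical examination and any specialist consultation. Preferably this is done by someone without access to follow-up weights, since the study is open. Report how many are unable and how many cannot be classified.
3. **Pre-specify one sensitivity analysis**: the primary analysis repeated with able controls only. The planned primary model stays unchanged.

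**Cost.** A short amendment and a smaller control pool, or a review of 30 records. Under the assumed contrasts the restricted confidence interval (log scale) is about 2-4% wider than planned with 27 controls and 8-14% wider with 21. The RMSE comparison is why this should not replace the primary analysis.

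**Limit.** Classification will be imperfect. If records identify only half of the unable controls, the remaining unable share is 0.05/0.95 = 5.3% (*f* = 10%) or 0.15/0.85 = 17.6% (*f* = 30%). With 25% / 10% response this leaves an OR of 3.13 (+4%) or 3.47 (+16%).

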10.1 Withdrawal of Consent form

Patients may voluntarily withdraw consent to participate in the study for any reason at any time.

Withdrawal of consent occurs only when a patient does not want to participate in the study anymore and does not want any further visits or assessments and does not want any further study related contacts and does not allow analysis of already obtained biologic material.

The patient from active group will be considered as terminated the study provided he/she missed three group classes in a row in the first 12 weeks.

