Premature subject/patient withdrawal	Point/time when the patient exits from the study prior to the planned completion of all study treatment administration and/or assessments; at this time all study treatment administration is discontinued and no further assessments are planned, unless the patient will be followed for progression and/or survival
Study discontinuation	Point/time when patient permanently stops taking study/investigational treatment for any reason; may or may not also be the point/time of premature patient withdrawal
Subject Number	A number assigned to each patient who enrolls into the study
Variable	A measured value or assessed response that is determined in specific assessments and used in data analysis to evaluate the drug being tested in the study

4 Protocol synopsis

Protocol number	
Title	Interventional study of active weight management in patients with type 2 diabetes and obesity in routine clinical practice during 12 months
Brief title	Feeling better together
Sponsor	Novartis
Investigation type	Non drug
Study type	Interventional study
Purpose and rationale	This study is aimed to achieve of long-term weight loss in T2DM patients by use of comprehensive lifestyle changes program, providing patients with structured diet, exercise plan, group behavioral support and group education. Additionally the study is designed to establish reduction of the body weight leads to the improvement of glycemic and lipid metabolism, and can also reduce blood pressure level. The study is also directed to show that lifestyle changes program in T2DM patients can lead to decreasing of hospitalization rate and healthcare consumption. In order to demonstrate a change from standard of care, data will be collected from a parallel cohort from the same centers.
Primary Objective(s) and Key Secondary Objective	The primary objective of the study is to demonstrate that comprehensive lifestyle changes program for patients with T2DM can lead to clinically significant weight reduction ($\geq 5\%$) compared with baseline in 12 months of observation.
Secondary Objectives	The secondary objective is to show that intensive lifestyle changes program for patients with T2DM can lead to: 
 • weight reduction compared with baseline in 3, 6, 9 months of observation • improved glycemic control: HbA1c and FPG • improved blood pressure level • improved lipid profile • improved QoL

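### Active patients who miss three classes in a row leave the study with no later weight scheduled, so their month-12 status in the primary analysis rests on a carried-forward weight from about week 9 or earlier

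*Protocol*

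**What the plan says.** The rule appears in three places. Protocol 10.1 states that an active patient "will be considered as terminated the study provided he/she missed three group classes in a row in the first 12 weeks". Protocol section 8 says "The drop-out criteria is three in a row missed group classes in the first 12 weeks of the study in active group", and SAP section 6 repeats it as the definition of drop-out.

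The Protocol glossary says of premature withdrawal that "at this time all study treatment administration is discontinued and no further assessments are planned", except for follow-up of progression or survival. It defines stopping study treatment separately, as a point that "may or may not also be the point/time of premature patient withdrawal". Protocol 10.1 reserves withdrawal of consent for patients who want no further visits, assessments or contact.

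On numbers, Protocol section 8 says "Drop-out of patients is expected for about 20% of patients" and "The drop-out in control group is not expected". Controls are invited at months 3, 6, 9 and 12 (Protocol section 10).

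The primary endpoint is a loss of at least 5% at 12 months (Protocol 6.3, SAP 5.1). Protocol section 10 gives the aim as "to reduce weight no less than 5% compared with the baseline in the first three months and then to maintain the positive dynamics" over the next nine months.

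The primary analysis uses the Full Analysis Set (FAS) with LOCF (SAP sections 7, 8 and 12.1). The FAS needs a baseline and at least one later efficacy value, with no attendance condition. The sensitivity analyses are a Per Protocol (PP) analysis and a generalized estimating equations (GEE) model without imputation.

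**The concern.** Failing to attend classes is not a refusal to be weighed. The glossary keeps stopping the intervention apart from leaving the study, but Protocol 10.1 and section 8 merge the two for class non-attenders. Data collection therefore stops in patients who may still consent to it, and it stops because of adherence to the programme under test.

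The rule can act only in the first 12 weeks and only in the active group. A patient it removes has no planned weight in the nine-month maintenance phase, which is what a 12-month endpoint is meant to capture. Two examples show the effect. A patient at −6% in week 5 who then stops attending is a month-12 responder under LOCF, even if the weight is later regained. A patient at −2% in week 3 who then stops attending is a non-responder, even if more weight is later lost. No analysis can recover a weight that was not taken.

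**Working it through.** **Inputs from the documents.** 100 active and 30 control patients; drop-out about 20%, none expected in controls (Protocol section 8); classes once a week for 12 weeks and observation to week 48 (Protocol section 10); LOCF in the FAS (SAP section 8). The documents give no responder rates, so all responder rates below are assumptions. The stated 80% power cannot be reproduced because no standard deviation or responder rate is given; this point does not depend on it.

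**1. Is a later weight scheduled?** Protocol 10.1 ends participation, the glossary plans no further assessments after premature withdrawal, and the active-group visit schedule makes no separate provision for terminated patients. The answer is no.

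**2. Age of the carried-forward weight.** Assume one class session per week and that a missed class means a missed weighing. Three consecutive misses among 12 classes are at the latest classes 10, 11 and 12, so the last attended class is class 9 or earlier. The gap to week 48 is at least 48 − 9 = 39 weeks.

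**3. Number affected.** 0.20 × 100 = 20 active patients, if the drop-out is all active. As a plausibility check, if classes are missed independently with probability q, the chance of a run of at least three misses in 12 is:

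| q | Chance |
|---|---|
| 0.2 | 6.5% |
| 0.3 | 18.9% |
| 0.4 | 37.3% |

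A figure near 20% could arise from this rule alone.

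**4. Error in the planned LOCF estimate.** Error in the active proportion = 0.2 × (rate carried forward − true month-12 rate) in the terminated patients:

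- 20% carried forward, 0% true: 0.2 × 20 = +4 points
- 10% and 10%: 0 points
- 0% carried forward, 20% true: 0.2 × (−20) = −4 points

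The sign is not fixed.

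**5. What the observed data alone can say.** Count the 20 unobserved patients first as all non-responders, then as all responders. The odds ratios are unadjusted, against an assumed 3/30 control responders:

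| Response in the 80 observed (assumed) | Responders | Active proportion, lower to upper | Odds ratio, lower to upper |
|---|---|---|---|
| 50% | 40 | 40/100 to 60/100 | 6.0 to 13.5 |
| 30% | 24 | 24/100 to 44/100 | 2.8 to 7.1 |

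The range is 20 points wide in both rows.

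**6. Do the sensitivity analyses cover this?** PP excludes patients without primary-endpoint data. The GEE uses observed values only, so its month-12 estimate rests on patients still attending. A completers-only estimate exceeds the full-group value by 0.2 × (completer rate − terminated rate). With completers at 50% and terminated patients truly at 0, 10, 20 or 30%, the excess is 10, 8, 6 or 4 points. Both analyses lean towards adherers, and neither takes the unfavourable case for the terminated patients.

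**7. Effect of the fix.** If 15 of the 20 (an assumed three quarters) return at week 48, 5 of 100 remain unknown and the range narrows from 20 points to 5.

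**The case against.** A reader might infer that the trial's main answer comes from an adherence-selected active group compared with a fully followed control group. The documents do not support that. The FAS has no attendance condition and weight is planned weekly, so most terminated patients stay in both numerator and denominator. Selection on adherence is confined to the PP analysis, the no-imputation GEE, and patients who leave before any post-baseline value. Complete control follow-up is a planning expectation only, and SAP section 8 applies LOCF to controls too. Nor is upward bias established; step 4 shows either direction.

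Other objections have some force:

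- The glossary text reads like a template: its exception for progression and survival does not fit this trial. The SAP also computes programme duration separately from study duration (section 11). The absence of later weighing is therefore inferred, but no section provides for it.
- Protocol Table 7-1 lists four kinds of class each week, and the documents do not say whether three in a row counts sessions or weeks. If sessions, the last weight could be somewhat later than week 9; a week-12 weight would still be 48 − 12 = 36 weeks old.
- The overall conclusion may survive. At the 40/100 lower bound against an assumed 3/30, Fisher's exact p is 0.002. At 24/100 it is 0.13 against 3/30 and 0.04 against 2/30, so the risk is real only in some scenarios.
- Counting terminated patients as non-responders would report the lower bound with no new visits. That is useful, but it does not replace a measured outcome.

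**Conclusion.** The point holds in this form: for a reason tied to adherence, and in the active group only, the plan leaves the month-12 weight uncollected in patients who have not necessarily withdrawn consent. This affects about 20 of 100 active patients if the expected drop-out is all active. The primary analysis fills the gap with a weight at least about 39 weeks old (one class session per week assumed), with bias of unknown sign. The true active proportion is then known only to within 20 points: 40–60% or 24–44% at assumed observed response rates of 50% or 30%. These bounds describe what is unknown about the terminated patients; they are not an estimate of the error in the planned result. The planned sensitivity analyses do not close the gap. Measuring the outcome is cheap and uses visits that already exist for controls, so the change is worth making.

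**What to change.** In Protocol section 8 and 10.1 and in SAP section 6, record three consecutive missed classes as discontinuation of the class programme, not as termination of data collection. Unless consent is withdrawn, invite these patients to weight assessments at months 3, 6, 9 and 12, and at minimum to the week-48 weighing. State in SAP sections 8 and 12.1 that these measured weights are used in the FAS primary analysis in place of carried-forward values. For patients still without a month-12 weight, add a sensitivity analysis that counts them as non-responders.

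Two wording points belong in the same edit. Say whether three in a row counts sessions or weeks. Reconcile the drop-out rule (three missed classes) with the PP exclusion in SAP section 7 (more than three).

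The cost is a short protocol amendment, matching SAP text, and at most four routine weighings for each of about 20 patients (4 × 20 = 80 visits), with no new procedure. Some patients will not return, and the active responder rate may move in either direction.
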